7.5.5. EQ-5D-3L Questionnaire

The questionnaire will be analyzed according to the recommendations of the authors (see www.euroqol.org). EQ-5D consists of 2 pages – a 5 dimension descriptive system and the EQ visual analogue scale. A copy of the questionnaire is provided in Appendix D.

The descriptive system contains 5 categories: mobility, self-care, usual activities, pain/discomfort and anxiety/depression. These categories are scored on a scale of 1 to 3, with 1 being the best response, and 3 being the worst response. A total score can also be calculated for the EQ-5D-3L questionnaire. For ease of interpretation, these scores will be transformed into a 0-100 scale by using the following steps:

- Sum all of the sub-category scores (can take values from 5-15) and divide by the maximum possible score overall (3 x 5 categories = 15). If all questions within each sub-category are missed, exclude these from analysis.
- The total score is calculated as: $100 * (\text{subject total score} / \text{maximum possible score})$

The 5 categories and total will be summarized for the observed response and change from the study 8HA01EXT baseline for the FAS. See Section 5.1.3 for details of when questionnaire results should be excluded from tabulated summaries.

The EQ visual analogue scale is a visual scale from 0-100 to record a respondent's overall self-rated health state. The respondent is asked to mark an 'X' on the scale then record the corresponding number; 0 refers to the worst possible health state, 100 refers to the best possible health state. This will also be presented alongside the 5 dimension descriptive system scores. The EQ visual analogue scale will be summarized for the observed response and change from the study 8HA01EXT baseline for the FAS. See Section 5.1.3 for details of when questionnaire results should be excluded from tabulated summaries.

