5.1.3. Handling of Missing Data

Aside from the following, no imputation of study data will be performed.

- The episodic treatment regimen at the start of study 8HA01EXT will be imputed for the scenario specified in Section 5.3.1.
- The end of PK period of the parent study (997HA307 or 997HA309) and start of study 8HA01EXT will be imputed for the scenario specified in Section 5.3.1.
- The occurrence of a new bleeding episode will be imputed if >72 hours lapse between 2 consecutive injections administered to treat a bleed. Details are provided in Section 7.1.1.

For CHO-KLAT, if a subject has data missing at a particular visit, the total score can still be estimated provided at least 27 of the 35 questions have been answered. If a subject's data cannot be used to calculate an overall score that subject will also be excluded from summaries of individual domains at that visit and will be flagged as excluded from summaries in analysis dataset. Details are provided in Section 7.5.3 and Appendix E.

For HAEMO-QoL and HAEM-A-QoL, Hemo-Sat, EQ-5D-Y and EQ-5D-3L, if a subject has data missing at a particular visit for a domain, the total score and subscores will still be estimated provided the questionnaire makes provision for missing domains in the calculation algorithm of overall score. If a subject's data cannot be used to calculate an overall score that subject will also be excluded from summaries of individual domains at that visit and will be flagged as excluded from summaries in data listings. Details are provided in Sections 7.5.1, 7.5.2, 7.5.4 and 7.5.5 Appendix C, F, G, and D, respectively.

For the analysis of AEs and concomitant medications/procedures, if the stop/start date of an AE/concomitant medication is missing or partial, the corresponding study day will be left blank. However, inferences will be made from the partial and missing dates to classify medications as concomitant, AEs as treatment emergent (or not) and AEs during surgical/rehabilitation period. These inferences are described in Sections 6.4.1 and 8.2, respectively.

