APPENDIX C. SCORING ALGORITHM FOR HAEM-A-QOL AND HAEMO-QOL

Per the algorithm on <http://www.haemoqol.de/manual.htm>, to correctly score the questionnaires, each version has to be identified and the appropriate scoring list has to be selected. Basically high score represent low quality of life and scoring involves the following steps:

1. Assigning numbers to the response scale, which is applicable to both age groups (children and teenagers aged 13-16 and adults>16)

1= never, 2=rarely, 3=sometimes, 4=often, 5=all the time

For negatively worded items, the above classification can be applied in which higher values represent a lower quality of life. For positively worded items, the score has to be recoded (see below).

2. Recoding positively worded items

Positively worded items in the subscales table have to be recoded so that numeric values assigned are reversed:

1=all the time, 2=often, 3=sometimes, 4=rarely, 5= never

By recoding, high scores in positively worded items reflect not higher but lower quality of life. The then unidirectional values can subsequently be added to yield the summed scores according to the Scoring list for the respective questionnaire.

3. Producing the Raw score

A Raw subscale score is produced by summing up all items within a subscale. Its range lies between the lowest possible (number of items (n) x 1) and highest possible (number of items (n) x 5) value of the respective scale.

The Raw total score is produced by the addition of all items (instead of the subscale items only) of the questionnaire (again paying attention to the recoding procedure – see steps 1 and 2).

4. Transferring a raw score to a Standardized score

A Standardized score is produced by dividing the raw score by the number of items in the sub scale or total. This allows comparison between subscales.

5. Transferring a raw score to a Transformed Score between 0 and 100

Creating a transformed score makes it possible to express the score as a percentage between the lowest (0) and the highest (100) possible value. To obtain the transformed score the following transformation rule has to be applied:

Transformed score = $100 \times ((\text{raw score} - \text{minimal possible raw score}) / \text{possible range of raw scores})$
where:

- minimal possible raw score = number of questions answered \times 1
- maximal possible raw score = number of questions answered \times 5
- possible range of raw scores = maximum possible raw score - minimal possible raw score

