Example: A raw score of 20 on the “Physical Health” Scale is to be transformed:

- when all 7 questions were answered:
 - minimal possible score = 7
 - maximal possible score = 35
 - range of scores = 28
 - $TSS = 20 - 7/28 = 46.4$
- when 6 of the 7 questions were answered:
 - minimal possible score = 6
 - maximal possible score = 30
 - range of scores = 24
 - $TSS = 20 - 6/24 = 58.3$

Transformed scores can be produced from raw subscale and raw total scores.

The total transformed score will be presented in outputs.

6. Presentation of scores

The transformed scores for subscale and total will be presented in the outputs.

7. Subscales

The following sub score categories are included for the HAEMO-QoL (Children and Teenagers aged 13-16) questionnaire:

Time Period	Sub-scores for HAEMO-QoL	No. of questions	No. of non-missing items required to calculate subscale
During the past month	1. Physical health	7	6
	2. Feeling	8	6
	3. View of yourself	10	8
	4. Family	8	6
	5. Friends	4	3
	6. Perceived Support	4	3
	7. Other person	6	5
	8. Sports and School	9	7
	9. Dealing with Hemophilia	7	6
	10. Treatment	8	6
	11. Future	4	3
	12. Relationships	2	2
	Total Score	77	63

The following sub score categories are included for the HAEMO-A-QoL (Adults) questionnaire:

Time Period	Sub-scores for HAEM-A-QoL	No. of questions	No. of non-missing items required to calculate subscale
During the past month	1. Physical Health	5	4
	2. Feeling	4	3
	3. View of yourself	5	4
	4. Sports and leisure	5	4
	5. Work and school	4	3
	6. Dealing with hemophilia	3	3
	7. Treatment	8	6
Recently	8. Future	5	4
	9. Family planning	4	3
	10. Partnership and sexuality	3	3
	Total Score	46	38

8. Sub score Items

Provided below is a copy of both questionnaires. Items are highlighted when they require re-coding as detailed in point 2 above.

HAEMO QoL Child and Teen Questionnaire

[III,kids,long] – CIII-HAEMO-QOL-USA/English –Final Version-29 Jun 07

HAEMO - QOL

Questionnaire for Children and Teenagers

Kids' long Version

age: 13-16

Hello there!

We would like to find out how you have been feeling during the past weeks, so we have worked out a few questions that we would like you to answer.

This questionnaire was designed for teenagers with hemophilia.

⇒ Please read each question carefully.

⇒ Think about how things have been for you over the past weeks.

⇒ Choose the answer that fits you best and put an "X" in the appropriate box.

There are no right or wrong answers. It's what you think that matters.

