APPENDIX F. HEMO-SAT SCORING ALGORITHM AND QUESTIONNAIRE

The Hemo-Sat Patient Satisfaction scale is a 35-item questionnaire encompassing 6 subscales regarding the subject's and parent/caregiver's satisfaction with various aspects of the treatment and care the subject.

1. Scoring

The items presented in the Hemo-Sat questionnaire are worded in both positive and negative directions whereas the responses to the questions are consistently scored as 1=Totally agree, 2=Somewhat agree, 3=Neither agree nor disagree, 4=Somewhat disagree, and 5=Totally disagree. Therefore, the negatively-worded questions need to be rescored as 5=Totally agree, 4=Somewhat agree, 3=Neither agree nor disagree, 2=Somewhat disagree, and 1=Totally disagree so that a high score represent a high satisfaction with the treatment. After the rescoring the unidirectional values can be added to yield 6 subscores and a total score.

Negatively worded questions include numbers 9 through 11. The 32 remaining questions are all positively worded.

2. Producing the raw total and subscale scores

The raw total score is produced by summing up all of items that were answered across all 35 questions. Its range lies between the number of items answered \times 1 and the number of items answered \times 5. The highest possible score is 175. Applying a minimum data rule of 75%, at least 27 questions must be answered in order to obtain a total score.

Similarly, a raw subscale score is produced by summing up all items that were answered within a subscale. The range of values lies between the number of items that were answered \times 1 and the number of items that were answered \times 5 in a given subscale. The minimum number of questions answered for each subscale, applying a minimum data rule of 75%, is as follows:

Hemo-Sat Subscale	Number of questions	Number of non-missing items required to calculate subscale
1. Ease and convenience	11	9
2. Efficacy	6	5
3. Burden	4	3
4. Specialist/Nurses	7	6
5. Center/Hospital	5	4
6. General satisfaction with the treatment	2	2
Total score	35	27

3. Transferring a raw score to a Standardized (average) score

The Standardized score is the average of all items with a nonmissing score. That is, missing items do not contribute to either the numerator or denominator. This effectively imputes the

mean of all nonmissing items for the items that are missing, allowing for a comparison between subscales.

4. Transferring a raw score to a Transformed Score between 0 and 100

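### The EQ-5D-3L total in SAP 7.5.5 is described as a 0-100 score, but its formula runs from 33.3 to 100

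*SAP*

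**What the plan says.** SAP 7.5.5 scores each of the five EQ-5D-3L dimensions from 1 (best) to 3 (worst) and adds a derived total. On range it says "these scores will be transformed into a 0-100 scale by using the following steps". The first step is "Sum all of the sub-category scores (can take values from 5-15) and divide by the maximum possible score overall", with that maximum given as 15, and the quotient is multiplied by 100. The total is to be summarized in the FAS as observed value and as change from the extension-study baseline. Its direction is not stated. The VAS in the same section runs from 0 (worst) to 100 (best).

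On missing answers, 7.5.5 says only: "If all questions within each sub-category are missed, exclude these from analysis".

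The other questionnaires use a different transformation. Appendix C starts from "minimal possible raw score = number of questions answered" times 1, subtracts that minimum from the raw score and divides by the possible range. Appendices E and F do the same.

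SAP 5.1.3 adds a rule that opens "For HAEMO-QoL and HAEM-A-QoL, Hemo-Sat, EQ-5D-Y and EQ-5D-3L, if a subject has data missing at a particular visit for a domain". The total and subscores are still estimated where the questionnaire's algorithm provides for missing domains. If no overall score can be calculated, "that subject will also be excluded from summaries of individual domains at that visit", and the subject is flagged in the data listings. Appendix C has a column headed "No. of non-missing items required to calculate subscale", and Appendix F gives similar subscale minimums. For the Hemo-Sat total, Appendix F requires that "at least 27 questions must be answered in order to obtain a total score".

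**The concern.** The stated scale and the stated formula disagree within one section of the SAP. A transformation introduced to make the score easier to read gives a subject with no problems at all a score of 33.3. A reader who takes the 0-100 label at face value will see that as a third of the way to the worst state, or, reading it in the VAS direction, as poor health. Mean changes in the total will also look smaller than they would on the scale described.

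The 5.1.3 rule prompts a second, lesser question. A missed total can keep domains that meet their own minimum out of the summary tables.

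**Working it through.** **Inputs.** Five dimensions scored 1 to 3, divisor 15, multiplier 100 (SAP 7.5.5); range-based transformation (Appendices C, E, F); domain sizes and minimums (Appendices C, F).

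**1. The plan's own figures.** The raw range reproduces: 5 x 1 = 5 and 5 x 3 = 15. The 0-100 range does not:

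- lowest: 100 x 5/15 = 33.3
- highest: 100 x 15/15 = 100

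**2. Comparison with the transformation used elsewhere.** Applied to EQ-5D-3L, the Appendix C, E and F formula is 100 x (sum - 5)/(15 - 5).

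| Complete form | Sum | As written, 100 x sum/15 | Range-based, 100 x (sum - 5)/10 |
|---|---|---|---|
| All dimensions at level 1 | 5 | 33.3 | 0 |
| Three levels worse | 8 | 53.3 | 30 |
| All dimensions at level 2 | 10 | 66.7 | 50 |
| All dimensions at level 3 | 15 | 100 | 100 |

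One level moves the score by 100/15 = 6.7 points as written and by 100/10 = 10 points on the range-based scale, a ratio of 2/3. A three-level change shows as 20 instead of 30. The two versions are linked by: written score = 33.3 + (2/3) x range-based score. The relation is linear and increasing, so with complete data the ranking of subjects and the sign of every change are the same.

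**3. What uses the formula.** Only the derived total. The five categories are summarized on their own 1-3 scores, and the VAS is recorded directly from 0 to 100.

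**4. A blank dimension.** The text does not say whether the dimension or the whole form is excluded. Suppose only the dimension drops out:

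- divisor kept at 15, four answers at level 1: 100 x 4/15 = 26.7
- divisor changed to 12: 100 x 4/12 = 33.3

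The first would rate an incomplete form as better than a complete no-problem form. If the whole form is excluded, neither value arises.

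**5. The 5.1.3 rule.**

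- Hemo-Sat has 35 items in domains of 11, 6, 4, 7, 5 and 2. If only the 11-item ease and convenience domain is blank, 35 - 11 = 24 answers remain. That is below 27, so five complete domains leave the tables.
- Haem-A-QoL needs 38 of 46. No single blank domain loses the total (46 - 8 = 38), but physical health plus feeling does (46 - 5 - 4 = 37). The domain minimums sum to 37, so a form can meet all ten and still miss the total.
- Haemo-QoL needs 63 of 77. No single blank domain loses the total (77 - 10 = 67), but physical health plus feeling does (77 - 7 - 8 = 62). The domain minimums sum to 61, again below the total minimum.

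These are possible patterns. The documents do not say how often they occur.

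**The case against.** The strongest reply on the EQ-5D-3L total is that percent of maximum is a legitimate linear rescaling which loses no information, so only the label is wrong. That is fair as far as it goes: relabelling the range as 33.3-100 would remove the contradiction. It would still leave this total on a different footing from the transformed scores in Appendices C, E and F, and its direction would still be unstated beside a VAS that runs the opposite way.

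A reader might infer that every EQ-5D-3L change from baseline is shrunk. The documents do not support this, because neither the category scores nor the VAS passes through the formula. A reader might also take the 26.7 example as a demonstrated error. It depends on one reading of an unclear sentence, so it supports only a request to state the rule.

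On 5.1.3, a reader might infer that the plan contradicts its own appendices or throws usable scores away. Neither holds. The appendices say when a subscale can be calculated. Section 5.1.3 says when results enter the tabulated summaries, and 7.5.2 and 7.5.5 refer to it for that purpose. A total minimum stricter than the domain minimums is not a contradiction. The rule keeps totals and domains on a common set of subjects, and excluded subjects are flagged and stay in the listings. It is a prespecified choice with a cost, not an arithmetic mistake.

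**Conclusion.** The EQ-5D-3L point stands as an error of wording or formula in SAP 7.5.5. On complete forms the total described as 0-100 spans 33.3 to 100, and its changes appear at two-thirds of their 0-100 size. This follows from the SAP's own numbers. The only judgement is that the 0-100 description is what was intended, which the consistent use of the range-based formula in the appendices supports.

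The severity is minor. The EQ-5D-3L total is a descriptive patient-reported outcome with no formal testing, and the primary and secondary endpoints do not use it. Relaxing 5.1.3 is an optional improvement. How many domain scores it would return to the tables, and in which direction the means would move, cannot be determined from the documents.

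**What to change.** In SAP 7.5.5:

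- Calculate the total as 100 x (sum - 5)/10 when all five dimensions are answered. At minimum, keep the present formula and give its range as 33.3-100.
- State that a higher total means worse health, opposite to the VAS.
- State that the total is missing when any dimension is blank.

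Optionally, in SAP 5.1.3, let each Haem-A-QoL, Haemo-QoL and Hemo-Sat domain enter the summary tables when its own Appendix C or F minimum is met, even if the total cannot be calculated. The same sentence could let answered EQ-5D-3L dimensions be summarized when the total is missing; otherwise the new missing-total rule would remove them under 5.1.3 as it stands. No change to the item minimums is proposed.

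The cost is SAP wording and scoring code, with no new data. The optional change has one drawback: totals and domains would then rest on different subjects, so n should be shown for each.

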7.5.6. Health-Economic Parameters

Health-economic assessments consist of the following items based on the time period since the last visit at which they were assessed:

- Number of hospitalizations excluding planned hospitalizations, elective surgery documented at Visit 1, and emergent surgery

- Number of emergency room visits
- Number of physician visits, excluding study visits
- Number of hospitalization days
- Number of days off work, school, day care, or preschool
- Number of days off work for the parent or caregiver

The previous visit for the Visit 1 refers to the previous visit in the parent study where applicable.

These data will be tabulated categorically at each visit for overall treatment regimen for the FAS.

Information collected on the questionnaire relates to both hemophilia and non-hemophilia related events. Thus, in addition to summarizing the hemophilia-related health resource utilization, the utilization for hemophilia- and non-hemophilia related events will be combined and the total summarized for the last 4 assessments listed above.

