7. STUDY DESIGN

7.1. Study Overview

This is an open-label, multi-center, long-term study of IV administration of rFVIII Fc in previously treated patients (PTPs) with hemophilia A who have completed the A-LONG study (997HA301), the pediatric study (8HA02PED), or any other study with rFVIII Fc. This is a global study and will be offered to those countries participating in these studies.

Based on estimated sample sizes from these studies, approximately 194 subjects from the ongoing A-LONG study and the pediatric study may be eligible to enroll in this extension study. The End of Treatment (EOT) Visit of the previous study may serve as the initial visit of the extension study. Assessments performed at this visit will be used to confirm eligibility for participation in the extension study.

Study visits are scheduled at 6-month (± 2 weeks) intervals following completion of Visit 1. Unscheduled visits may occur as deemed necessary by the Investigator. For subjects who enter the extension study and undergo surgery before completing their Last Post-Operative Visit from the prior rFVIII Fc study, the Last Post-Operative Visit assessments will be performed when the subjects switch from their post-surgery dosing regimen to a regimen outlined in Section 5.3 (see Section 5.3.3 for list of assessments). For subjects who have fewer than 50 exposure days (EDs) with rFVIII Fc following completion of Visit 1, a visit may be conducted to perform inhibitor testing at the time subjects reach 10-15 EDs, 50-75 EDs, and 100-125 EDs, as applicable. If the timing does not coincide with a scheduled visit, an unscheduled visit may be conducted.

For subjects undergoing surgery, post-operative clinic visits may be more frequent. For subjects undergoing major surgery, a visit is required 1-2 weeks after surgery (Visit 3, not required for minor surgery). Visit 4 is required only if subjects who had major surgery did not return to a regular rFVIII Fc regimen as determined by the Investigator at Visit 3. All major surgeries will be reported as SAEs. Scheduled visits will include safety and efficacy assessments, and FVIII activity measurements to assess trough and peak (recovery) (Section 4). In addition, the site will continue to contact study subjects and/or caregivers by telephone on a bimonthly basis to review AEs, treatment compliance, and use of concomitant medications and therapies.

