11.2. Withdrawal of Subjects From Study

Subjects must be withdrawn from the study for any 1 of the following reasons:

- The subject and/or parent/guardian withdraw consent.
- The subject and/or parent/guardian are unwilling or unable to comply with the protocol.
- The subject meets any of the criteria defined in Section 11.1.

The reason for the subject's withdrawal from the study must be recorded in the subject's eCRF.

Subjects who discontinue study treatment and are withdrawn from the study will not be replaced.

If the decision is made to withdraw the subject from the study, the final study visit/early termination visit will be performed as described in Section 4 ([Table 1](#)).

CONFIDENTIAL

The information contained herein may not be used, disclosed, or published without the written consent of Biogen Idec MA Inc.

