16.5.2.2. Health Outcomes

Summary statistics of health outcome endpoints will be tabulated at each collection timepoint.

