Unless specified otherwise, for the purpose of analyses involving change from baseline during 8HA01EXT, baseline will be defined as the last non-missing measurement (that can be used for data analysis) taken prior to or on the date of 8HA01EXT study Study Day 1 (see Section 5.1.1 for a description of study days). Eligible subjects will be enrolled at End of Treatment (EOT) visit of their parent study (997HA301, 8HA02PED, 997HA307, or 997HA309), which will serve as the Baseline Visit for this extension study (Visit 1). Baseline visit assessments may have been repeated if there was a gap in study treatment (e.g. a gap of greater than 37 days following the EOT Visit for the previous study). Post-baseline values are defined as any assessment taken after 8HA01EXT Study Day 1 (see Section 5.1.1 for a description of study days). In the case of unscheduled visits being taken for the same visit number assigned, the latest available non-missing assessment for that visit will be used for by-visit summaries.

Data collected at the local laboratories will be excluded from the analyses of laboratory data but will be included in the data listing.

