6. STUDY SUBJECTS

6.1. Disposition of Subjects

Subject disposition will be summarized for study 8HA01EXT for subjects from each parent study and overall. This table will present the number of subjects in the All-enrolled Analysis Set, the number and percentage of subjects enrolled in the Full Analysis Set (FAS) including the number of subjects with an efficacy period, the number of subjects within each treatment regimen, the number and percentage of subjects in the Safety Analysis Set, and the number and percentage of subjects in the surgery subgroup. The number of subjects with the status of completed, and discontinued from the study, including the primary reason for those who discontinued, will be tabulated. Subject disposition, including the date of the last visit and the reason for early termination for subjects who did not complete the study, will be provided in a data listing.

The number and percentage of enrolled subjects will be summarized by country, site and treatment regimen using All-enrolled Analysis Set. The number of subjects attending each visit in study 8HA01EXT will be summarized overall by planned visit using the Safety Analysis Set. The summary for each study visit will include only those subjects for whom the visit evaluations reflect the designated visit on the study (i.e., including subjects for whom this visit represents the end-of-study visit due to early termination).

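### SAP 7.5.6 tabulates health-resource counts over a variable look-back with no time denominator, so records with unequal windows are not comparable

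*SAP*

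**What the plan says.** SAP 7.5.6 lists six counts: hospitalizations, emergency room visits, physician visits, hospitalization days, days off work or school, and days off work for a parent or caregiver. The time basis is stated once for all of them: "Health-economic assessments consist of the following items based on the time period since the last visit at which they were assessed". For the first extension visit it adds: "The previous visit for the Visit 1 refers to the previous visit in the parent study where applicable". The analysis is: "These data will be tabulated categorically at each visit for overall treatment regimen for the FAS".

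Protocol 16.5.2.2 adds nothing on time: "Summary statistics of health outcome endpoints will be tabulated at each collection timepoint". The regular spacing is in Protocol 7.1: "Study visits are scheduled at 6-month (± 2 weeks) intervals following completion of Visit 1". Protocol 11.2 allows a visit outside that grid: "If the decision is made to withdraw the subject from the study, the final study visit/early termination visit will be performed".

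Neither document gives a rate, a person-time denominator, a restriction on window length or a summary of days covered for these items. Other count-type data in the SAP are handled differently. Bleeding episodes (7.1.1) and consumption (6.5.4) are divided by days in the efficacy period and multiplied by 365.25. Where raw bleed counts are shown (7.3.1), total subject-years are given beside them as context.

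**The concern.** A count depends on how long one looks. If the look-back differs between records, a constant rate produces different counts, and a by-visit table can show a rise or fall that reflects only the time covered. Three routes to unequal windows are open here:

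- **Visit 1.** Its window starts in another study, at a visit interval that the documents do not state.
- **A missed assessment.** Because the window runs from the last assessment, the next record covers about 12 months instead of 6.
- **A final visit off the 6-month grid.** This can follow withdrawal. It can also follow a planned exit, because SAP 3.3.4 lets subjects leave when they switch to commercial product or expanded access.

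A fourth, conditional route is the rule in SAP 5.1 for unscheduled visits that share a visit number: "the latest available non-missing assessment for that visit will be used for by-visit summaries". If the items were asked again at such a visit, the retained record would cover only the short interval since the previous one.

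The study is descriptive, so the table itself is the result and no later model would correct it. What is at stake is how resource use over time is read, not a test or the primary endpoint.

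**Working it through.** The plan states no expected count, rate or sample size for these items, so there is no figure to reproduce. The check is an illustration.

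**Inputs**
- Scheduled window: 6 months, ± 2 weeks (Protocol 7.1).
- Window after one missed assessment: about 12 months (follows from SAP 7.5.6).
- Window at an off-schedule final visit: assumed 3 months.
- Visit 1 window: not in the documents. Taken as 3 to 6 months for illustration.
- Event rate r: not in the documents. Assumed constant, 0.25 to 4 per subject-year.
- Share of records with an unusual window: not in the documents. Assumed 10%, with 5% and 20% as a range.

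**Step 1. Effect of the window on one record.** For a Poisson count over T years, the expected count is r × T and P(at least 1) = 1 − exp(−r × T).

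| r per year | 3 months | 6 months | 12 months |
|---|---|---|---|
| 0.25 | 6.1% | 11.8% | 22.1% |
| 0.5 | 11.8% | 22.1% | 39.3% |
| 1 | 22.1% | 39.3% | 63.2% |
| 2 | 39.3% | 63.2% | 86.5% |
| 4 | 63.2% | 86.5% | 98.2% |

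The expected count doubles from 6 to 12 months and halves from 6 to 3, whatever the rate. The Poisson form suits events better than the items counted in days, which cluster. The proportionality of the expected count to time holds for all six items if the rate is constant.

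**Step 2. Visit 1 against a 6-month visit.**
- If the parent-study interval was 6 months, the difference is 0.
- If it was 3 months, the difference in points is 11.8 − 6.1 = 5.7 at 0.25 per year, 22.1 − 11.8 = 10.3 at 0.5, 39.3 − 22.1 = 17.2 at 1, 63.2 − 39.3 = 23.9 at 2, and 86.5 − 63.2 = 23.3 at 4.

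The documents cannot narrow this. Protocol 5.1.3 gives 102.05 person-years for 164 subjects in 997HA301, a mean of 102.05 / 164 = 0.62 years. That is time on study, not the interval between assessments.

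**Step 3. Unusual records inside a scheduled column, at r = 1.**
- 10% at 12 months: the mean is multiplied by 0.9 + 0.1 × 2 = 1.10. P(at least 1) = 0.9 × 39.3% + 0.1 × 63.2% = 41.7%.
- 10% at 3 months: the mean is multiplied by 0.9 + 0.1 × 0.5 = 0.95. P(at least 1) = 0.9 × 39.3% + 0.1 × 22.1% = 37.6%.
- With 5% of records the results are 40.5% and 38.5%. With 20% they are 44.1% and 35.9%.
- With 10% of each kind together, the shifts largely cancel: 40.0%.

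For scale, windows of 5.5 and 6.5 months, roughly the scheduled tolerance, give 36.8% and 41.8%.

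**Step 4. Effect of a time denominator.** In the column with 10% of records at 12 months and r = 1, expected events per record are 0.9 × 0.5 + 0.1 × 1.0 = 0.55. Time per record is also 0.55 years. The pooled rate is 0.55 / 0.55 = 1.0 per year, the true value.

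**The case against.** The strongest reply is that little depends on this table. The items are neither primary nor secondary endpoints, nothing is tested, and SAP 7.5.6 plans no change from baseline, unlike the questionnaire scores in 7.5.1 to 7.5.5. Counting since the last assessment also has a purpose: events are not lost when an assessment is missed. The footnotes to the protocol's schedule say that changes in health outcomes are queried in the eDiary on an ongoing basis, so the data do not rest on recall over a long interval alone. All of this stands. It limits the importance of the point but does not supply the missing denominator.

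Two stronger readings are tempting, and the documents do not support them.

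- **A reader might infer that separate early-termination and after-missed-visit columns are biased by construction.** SAP 7.5.6 sets out no such columns. The wording in SAP 6.1, "including subjects for whom this visit represents the end-of-study visit due to early termination", belongs to the visit-attendance summary, and it counts early terminators under the designated visit. If the same is done here, the effect is a mixture within scheduled columns, as in Step 3. A completer's final visit may also fall on the 6-month grid. Collection of these items at the final visit could not be confirmed, because the body of the schedule table (Protocol Table 1) is not in the text reviewed.
- **A reader might infer that resource use must appear to rise by 17 to 24 points after Visit 1.** That needs a 3-month parent interval and a rate of at least 1 per year. Neither is in the documents. At 0.5 per year the figure is about 10 points, and with a 6-month parent interval it is zero. A gap before entry does not necessarily lengthen the window either, because the parent study's End of Treatment visit may itself serve as Visit 1 (Protocol 7.2.1).

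**Conclusion.** The point holds in a limited form. SAP 7.5.6 uses a look-back that varies by definition and tabulates raw counts without the time they cover. Records with unequal windows are therefore not comparable at the same underlying rate. The SAP already gives its bleeding and consumption data a time denominator.

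The size is uncertain and probably modest. At Visit 1 the effect ranges from none upward, depending on an interval that is not documented. Within scheduled columns it is about 2 points in the share with at least one event. That figure assumes 1 event per year and 10% of records with 12-month or 3-month windows, and the final-visit part also assumes that the items are collected there. The primary endpoint is unaffected. This is a worthwhile low-cost improvement to a descriptive table, not a threat to the study's conclusions.

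**What to change.** In SAP 7.5.6:

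1. Keep the categorical table.
2. For each visit column, show the median and range of days covered, from the previous health-resource assessment to the current one.
3. Add a pooled rate for each item, total events (or days) / total days covered × 365.25, at each visit and over the whole extension.
4. Show Visit 1 separately, since its window lies in the parent study, and leave it out of the extension-wide rate.
5. State which column holds early-termination and final-visit records, if the items are collected there.

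Two further steps are not needed. Annualizing each subject's short window separately is unstable: one event in 14 days becomes 1 / 14 × 365.25 = 26.1 per year. Restricting the raw table to windows of 6 months ± 2 weeks would discard records.

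The cost is SAP wording and a small amount of programming. Visit dates are already collected, although Visit 1 needs the date of the previous parent-study assessment. Rates will be noisier where total person-time is short, and the days-covered display lets the reader see where that is.
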